8.4 Other Assessments

8.4.1 *Photography*

Photographs will be taken at baseline, prior to the first injection of the study product and at the follow-up visit at Day 15. The baseline photographs were used for the assessment CCI. The photographs could also be used to document AEs in the treatment area.

Camera equipment will be provided by the Sponsor and standardized photographs will be obtained according to detailed instructions in a separate photography user manual. Each hand will be photographed separately. Each Investigator and other study site personnel designated to take photographs, if applicable, shall be thoroughly trained in the equipment and techniques, and how to upload photographs to the secured web portal, if applicable, before study start. For further details, please see the instruction in photography user manual.

GALDERMA EST. 1981	Title 43CH2305 Statistical Analysis Plan	Doc id MA-59378
------------------------------	---	----------------------------------

Study Number 43CH2305
Statistical Analysis Plan

CONFIDENTIAL

Page 19 of 36
Final, 1.0, date 24APR2024

9 DERIVATION OF EFFECTIVENESS, SAFETY AND OTHER ENDPOINTS

[figure not shown]
9.1 Effectiveness Endpoints

9.1.1 Primary Effectiveness Endpoint

The primary effectiveness endpoint is the within-subject difference in VAS score at the end of injection (T0), and will be calculated as:

- $\Delta_{T0} = (\text{VAS score at T0 for the Restylane Skinboosters Vital Lidocaine hand}) - (\text{VAS score at T0 for the Restylane Vital hand})$.

CCI

2024-04-25 10:28

Effective date:

Effective

Version: 1.0

Study Number 43CH2305
Statistical Analysis Plan**CONFIDENTIAL****Page 20 of 36**
Final, 1.0, date 24APR2024

CCI

9.1.3 Exploratory Effectiveness Endpoints

Not applicable.

CCI

CCI

CCI

10 STATISTICAL METHODS AND DATA CONSIDERATIONS

10.1 General Considerations

10.1.1 Baseline

For statistical analyses purpose, baseline is defined as the last non-missing measurement prior to the first treatment.

Change from baseline will be calculated as follows:

Absolute Change from Baseline = PostBaseline – Baseline.

 EST. 1981	Title 43CH2305 Statistical Analysis Plan	Doc id MA-59378
---	--	---------------------------

Study Number 43CH2305
Statistical Analysis Plan

CONFIDENTIAL

Page 22 of 36
Final, 1.0, date 24APR2024

10.1.2 Missing and Partial Dates Management

10.1.2.1 *Missing and Partial Dates of Adverse Events*

While every effort will be made to obtain complete information on every reported AE, imputation will be made for any respective missing AE data for the purpose of calculating onset time and duration. Dates will be presented as is in the listings.

The following date imputation rules will be used.

- Start Date
 - If start date is completely missing, it will be assumed that the AE started at the treatment date.
 - If the start date is missing the day, the treatment day will be used.
 - If the start date is missing the month, the treatment month will be used, provided it is on or after the subject's treatment date; otherwise, the subsequent month after the treatment date will be used (i.e., if treatment date is 15-DEC-2023, and AE start date is 01-UNK-2023 then start date becomes 01-JAN-2024).
 - If the start date is missing the year, the treatment year will be used provided it is on or after the subject's randomization date; otherwise, the subsequent year after randomization will be used.
- End Date
 - If end date is completely missing, it will be assumed that the AE is still ongoing and will not be imputed.
 - If the end date is missing the day, the last day of the month will be used (i.e., UNK-JAN-2024 becomes 31-JAN-2024)
 - If the end date is missing the month, the subsequent month after the start date will be used.
 - If the end date is missing the year, the year of treatment will be used (i.e., 01-JAN-UNK becomes 01-JAN-2024), provided it is after the start date; otherwise, the subsequent year after start date will be used.

10.1.2.2 *Missing and Partial Dates of Prior/Concomitant Therapies and Prior Aesthetic Procedures or Implants*

As no calculations on start and stop dates will be done, no imputation of missing or partially missing dates will be performed.

GALDERMA <small>EST. 1981</small>	Title 43CH2305 Statistical Analysis Plan	Doc id MA-59378
---	---	----------------------------------

Study Number 43CH2305
Statistical Analysis Plan

CONFIDENTIAL

Page 23 of 36
Final, 1.0, date 24APR2024

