#### 12.1.2 Recording Instructions

AE will begin to be collected after ICF signed. Each subject will be questioned about AEs at each clinical visit following the screening visit. The question asked will be "Since your last clinical visit have you had any health problems?" Information on AEs can also be obtained from signs and symptoms detected during each examination or from a laboratory test, observations by the study personnel, subject diaries or spontaneous reports from the subjects.

When an AE is related to a device deficiency (refer to section 12.2), including technical device malfunction, the AE shall be recorded on the AE module in the eCRF and the technical complaint shall be reported separately on the clinical study complaint form.

Investigators, or other study personnel, will record all AEs in the eCRF, including:

- Event term (recorded in standard medical terminology and avoiding abbreviations),
- Description of event and affected area (if applicable),
- Start date (First day with symptoms)

 EST. 1981	Title 43CH2305 CSP Vital-Lido-Hand-2w	Doc id MA-57336
---	---	---------------------------

- Stop date (Last day with symptoms)
- Intensity (mild, moderate or severe according to definition in section 12.1.3)
- Seriousness (serious or not serious, according to definition in section 12.3)
- Causal relationship to study product and study product injection procedure (yes or no)
- Action taken (none, medication treatment, non-pharmacological treatment or other procedures/ tests, subject withdrawn)
- Outcome of the AE (ongoing, resolved, resolved with sequelae, death)

The AE module in the eCRF must be signed and dated by the Investigator.

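### Two adverse-event start-date rules in SAP 10.1.2.1 give wrong onset dates in identifiable cases: the missing-day rule at month ends and the missing-month rule at year ends

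*SAP*

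**What the plan says.** SAP 10.1.2.1 imputes adverse-event dates "for the purpose of calculating onset time and duration. Dates will be presented as is in the listings". For start dates:

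- Day missing: "If the start date is missing the day, the treatment day will be used". No condition is attached.
- Month missing: the treatment month is used if the result is not before treatment; "otherwise, the subsequent month after the treatment date will be used". The illustration is "if treatment date is 15-DEC-2023, and AE start date is 01-UNK-2023 then start date becomes 01-JAN-2024".
- Year missing: the treatment year is used if the result is not before randomization; "otherwise, the subsequent year after randomization will be used".
- Everything missing: the treatment date is used.

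The start rules do not refer to the recorded end date or to the last visit.

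Protocol 12.1.2 says "AE will begin to be collected after ICF signed", and screening may begin 14 days before Day 1, so an event can be recorded before treatment. The schedule of events puts the final visit at Day 15 (+3 days). SAP 10.6.1 summarizes time to onset and duration, by SOC and PT, for events related to the product or the injection procedure. SAP 10.1.3 derives an analysis day for events from the treatment date.

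**The concern.** An imputation rule for partial dates should respect what was recorded and return a date that could have happened. Two of these rules can fail that test. The missing-day rule can return a date after the subject has left the study, after the event's own stop date, or absent from the calendar. The missing-month rule, in the SAP's own illustration, contradicts the recorded year.

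What is at stake is the time-to-onset and duration tables for related events. At preferred-term level the counts may be small, so one artefact can set the maximum and move the mean. Protocol section 9 describes delayed onset in the earlier Chinese hand study as more than 21 days after the last treatment. An imputed gap of 28 to 31 days would look like such an event in a study that follows subjects for two weeks.

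**Working it through.** **Inputs.** The start-date rules come from SAP 10.1.2.1, and the screening window (14 days) and final visit (Day 15 + 3 = Day 18 at the latest) from the schedule of events. The treatment date is Day 1, so a date *k* days after treatment is Day *k* + 1, and a date *k* days before is Day −*k*. The treatment day is read as the day of the month, which matches the parallel wording for month and year. If it meant the full treatment date, a recorded later month would be overwritten instead.

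**1. The SAP's own illustration.** Treatment is 15-DEC-2023 and the start is 01-UNK-2023. The treatment month gives 01-DEC-2023, which is before treatment, so the next month is taken: 01-JAN-2024. That is 17 days after treatment, or Day 18, and the SAP's result is reproduced. But every first-of-month date in 2023 precedes 15-DEC-2023. The only one inside the collection window is 01-DEC-2023, Day −14. The rule changes the recorded year and moves the event 31 days.

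**2. Missing day, month after treatment.** Inserting the treatment day into the next month gives a gap equal to the length of the treatment month: 28 to 31 days, Day 29 to Day 32. All of these are beyond Day 18.

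- Treated 28-DEC-2023, start UNK-JAN-2024: 28-JAN-2024, 31 days later, Day 32.
- Treated 25-MAY-2024, start UNK-JUN-2024: 25-JUN-2024, Day 32. No year end is needed.
- Treated 31-MAY-2024, start UNK-JUN-2024: 31-JUN, which does not exist.
- First case with a recorded stop of 05-JAN-2024: 05-JAN minus 28-JAN = −23 days (−22 if both end days are counted).

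**3. How often the calendar allows this.** In 2024, the 14-day follow-up crosses a month end for the last 14 treatment dates of each month: 12 × 14 / 366 = 168 / 366 = 45.9%. This is a share of treatment dates, not an error rate. Now take every 2024 treatment date with true onset on Day 1 to Day 18, equally weighted: 366 × 18 = 6,588 pairs. Onset falls in the next month in 12 × (1 + 2 + … + 17) = 12 × 153 = 1,836 pairs, or 27.9%. If the day is missing, 26.3% of all pairs are dated past Day 18 and about 1.5% get a non-existent date. The other 72.1% get the treatment date.

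**4. Missing month, other cases.** For true post-treatment onsets on the same grid, 97.7% are dated exactly and 2.3% land past Day 18, at a year end. For example, treatment on 28-DEC-2023 with start 03-UNK-2024 gives 03-DEC-2024, Day 342, although 03-JAN-2024, Day 7, fits. Away from a year end no recorded part is overwritten, but a screening-period onset can still be pushed forward: treated 15-MAY-2024 with start 10-UNK-2024 gives 10-JUN-2024, Day 27, where only 10-MAY-2024, Day −5, lies in the window.

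**The case against.** The strongest reply is that very little of this reaches a table. Imputed dates serve onset time and duration only, and listings show dates as recorded. Those summaries cover related events, and an event before treatment should not be judged related to the product or its injection. The visible text has no treatment-emergent filter, so counts by SOC, PT, relatedness and intensity do not change. Partial dates should also be rare: subjects are asked about events at 72 hours and Day 15, the eCRF checks for incomplete data, and the SAP promises every effort to complete the record. All of that stands, and it limits the point.

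Several stronger readings are tempting, and the documents do not support them:

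- **That screening-period events contaminate the related-event summaries.** For the reason just given, the shift mainly affects analysis day.
- **That every partial date ends up weeks out.** A missing day in the treatment month returns the treatment date, a sensible choice since Protocol 12.1.8 says reactions typically begin that day. Most post-treatment onsets with the month or year missing land inside follow-up.
- **That the rules generally overwrite recorded parts.** Only the missing-month rule does so, and only across a year end. Protocol version 3.0 took effect on 2024-03-13 with about 16 weeks planned. No first-subject date is given, so the case may never arise.
- **That the SAP's illustration shows an onset after study end.** Day 18 is the last day of the final visit window.

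The reply does not cover the missing-day rule. That rule acts on genuine post-treatment, related events at any month end, and they do enter the onset and duration tables.

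**Conclusion.** The point holds as a minor one. The missing-day rule is wrong as written whenever the recorded month is the one after treatment: onset is placed 28 to 31 days after treatment or on a non-existent date, beyond the last visit and possibly after the recorded stop. This distorts the time-to-onset and duration summaries of related events. The missing-month rule and its illustration are wrong across a year end, with an effect mainly on analysis day.

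The individual dates follow from the SAP text, given the day-of-month reading. The 26.3% and related shares assume treatment dates spread evenly over 2024 and onsets spread evenly over Day 1 to Day 18. They are conditional on the date part being missing, and the documents do not say how often that will happen. The pre-treatment cases also need a gap between consent and treatment; none exists when both fall on the same day. The primary endpoint, event counts and listings are unaffected.

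**What to change.** Replace the start-date bullets in SAP 10.1.2.1 with one rule:

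1. Keep every recorded date part.
2. Impute the earliest valid calendar date on or after the treatment date that fits the recorded parts and is not later than the recorded end date or the last contact.
3. If the recorded parts allow only pre-treatment dates, impute the latest compatible date between consent and the day before treatment, and flag the event as pre-treatment.
4. State that when the recorded parts fit both periods, the event is treated as post-treatment by convention.

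Remove or correct the 01-JAN-2024 illustration. Under this rule it becomes 01-DEC-2023, Day −14, if consent had been given by then. Treatment on 28-DEC-2023 with start UNK-JAN-2024 becomes 01-JAN-2024, Day 5, before the stop of 05-JAN-2024. Treatment on 31-MAY-2024 with UNK-JUN-2024 becomes 01-JUN-2024, Day 2.

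The rule does not resolve ambiguous records. In an enumeration of pre-treatment onsets with the day missing (Day −14 to Day −1, every 2024 treatment date, no recorded end date used), 75.4% are still placed on or after treatment because the recorded month fits both periods. The SAP should state this as a convention.

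The cost is SAP wording and a few lines of derivation code. No new data are needed.

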10.1.3 Reference Start Date and Analysis Day

The treatment date will be the reference start date.

Analysis day will be calculated from the reference start date and will be used to show start/end day of assessments, events, diseases, therapies, or procedures.

In the situation where the assessment/event/disease/therapy/procedure date is fully missing and cannot be imputed (i.e., when an adverse event, a disease, a therapy, or a procedure is reported as being ongoing), analysis day will be missing.

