10.6 Safety Analysis

10.6.1 Adverse Events

All AEs will be coded according to MedDRA and summarized by System Organ Class (SOC), Preferred Term (PT), including number of subjects with at least one event (n, %) and number of events.

For subject counts, a subject will only be counted once per SOC and once per PT in cases where multiple events are reported for a subject within SOC or PT. For event counts, subjects with multiple events in a category will be counted for each event.

The number of subjects with AEs related to study product or study product injection procedure, as well as unrelated AEs, will be presented by SOC, PT, and maximum intensity also including the number of events. Action taken for related AEs will be summarized by SOC and PT using number of events. Serious AEs will be listed.

For AEs related to study product or study product injection procedure, the number of days to onset and the duration of event will be summarized by SOC and PT using mean, standard deviation, median, minimum, and maximum.

In addition, a summary of all AEs will be provided, which will include (but is not limited to):

- frequency of subjects (n, %) with at least one AE and number of events (in total as well as serious AEs),
- frequency of subjects (n, %) with at least one related AE and number of events (in total as well as serious AEs),
- frequency of subjects (n, %) with at least one related AE in the hand treated with Restylane Skinboosters Vital Lidocaine, and number of events (in total as well as serious AEs),
- frequency of subjects (n, %) with at least one related AE in the hand treated with Restylane Vital, and number of events (in total as well as serious AEs),
- frequency of subjects (n, %) with at least one unrelated AE and number of events (in total as well as serious AEs),
- number of subjects who did not have an AE.

GALDERMA <small>EST. 1981</small>	Title 43CH2305 Statistical Analysis Plan	Doc id MA-59378
---	---	----------------------------------

Study Number 43CH2305
Statistical Analysis Plan

CONFIDENTIAL

Page 31 of 36
Final, 1.0, date 24APR2024

CCII

Page 10

CCI [REDACTED]

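### SAP 10.1.2.1: the end-month rule for partial AE dates makes same-month events about a month too long; the end-year and start-day rules fail in narrow cases (minor)

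*SAP*

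**What the plan says.** SAP 10.1.2.1 (Missing and Partial Dates of Adverse Events) gives one rule for each missing part of an AE date. Three matter here.

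- End month missing: "If the end date is missing the month, the subsequent month after the start date will be used". There is no proviso.
- End year missing: the year of treatment is used, "provided it is after the start date; otherwise, the subsequent year after start date will be used".
- Start day missing: "If the start date is missing the day, the treatment day will be used". There is no check against the recorded month or the AE end date.

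The start-month and start-year rules in the same list do have a proviso, and it is worded as *on or after*. Listings show AE dates as recorded.

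The imputed dates are used in SAP 10.6.1, where for related AEs "the number of days to onset and the duration of event will be summarized by SOC and PT", with mean, SD, median, minimum and maximum. They may also enter analysis day, which under SAP 10.1.3 "will be used to show start/end day of assessments, events, diseases, therapies, or procedures". Protocol 12.1.2 defines the recorded start and stop as the first and last symptomatic day, so a one-day AE has equal start and stop dates.

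**The concern.** A rule written to produce durations should not return one that the recorded date parts do not support. The end-month rule moves the end to the following month even when the recorded day fits the start month. The end-year proviso excludes equality, although equality is how a one-day AE is recorded. The start-day rule can place the start after the end.

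The safety duration table is what is at stake. In a preferred term with few events, one reaction of a few days shown as a month or a year can drive the mean, SD and maximum.

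**Working it through.** **Inputs.** The rules are those of SAP 10.1.2.1, applied literally. The SAP gives no duration formula, so I assume duration = end − start + 1 day. Protocol and SAP give no enrolment dates and no duration for related AEs. I therefore assume one start (or treatment) date on each of the 365 days from 01-MAY-2024 to 30-APR-2025, and vary the true duration L.

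**The SAP's own examples.** Treatment 15-DEC-2023 with start 01-UNK-2023 gives 01-JAN-2024, and end UNK-JAN-2024 gives 31-JAN-2024. Both reproduce. End 01-JAN-UNK becoming 01-JAN-2024 reproduces through the fallback clause when treatment and AE start are both in 2023.

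**(a) End month.** Start 10-MAY, end 12-UNK: the rule gives 12-JUN, which is 34 days; 12-MAY is 3 days.

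For L up to 28 days the rule fails exactly when the AE ends in its start month. A month of m days has m − (L − 1) such start dates, so over the year the count is 365 − 12(L − 1).

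| True duration L | Arithmetic | Fails | Right |
|---|---|---|---|
| 1 day | 365 − 0 | 365 | 0 |
| 3 days | 365 − 24 | 341 | 24 |
| 14 days | 365 − 156 | 209 | 156 |
| 28 days | 365 − 324 | 41 | 324 |

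In each row, 7 of the failures are dates that do not exist (true ends on 29, 30 or 31 January and on 31 March, May, August or October). The others are 28 to 31 days too long.

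Effect on a mean: ten 3-day AEs with one imputed at 34 days give (9 × 3 + 34)/10 = 6.1 days instead of 3.0.

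**(b) End year.**

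- Start 10-MAY-2024, end 10-MAY-UNK: the treatment year gives 10-MAY-2024, which is not *after* the start, so the rule moves to 10-MAY-2025. That is 366 days instead of 1, and it happens for 365 of 365 one-day AEs.
- For 2- to 4-day AEs starting on the treatment day, the rule is wrong for 0 of 365.
- With onset 2 or 14 days after treatment it is wrong for 2 or 14 of 365. These are the treatment dates whose AE starts in the next calendar year. Example: treatment 28-DEC-2024, start 05-JAN-2025, end 10-JAN-UNK becomes 10-JAN-2026, 371 days instead of 6.

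**(c) Start day.** Treatment 28-MAY, start UNK-JUN, end 05-JUN.

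- If *treatment day* means the day of the month, the start becomes 28-JUN, 23 days after the AE ended.
- If it means the full treatment date, 28-MAY contradicts the recorded June.

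On the first reading, with onset 2 days after treatment and AEs of 1 to 7 days, 24 of 365 treatment dates put the start in the next month: 18 give a start after the end, 6 give a non-existent date, none is right. When the AE starts in the treatment month, the rule gives the treatment date, and I do not dispute that.

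**The case against.** **Partial dates should be rare.** The SAP promises every effort to obtain full dates, and Protocol 8.1 and 8.2 provide logical checks and manual review. This stands as a limit on frequency. It does not make the rules right for the dates that remain partial.

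**Longer AEs favour the SAP rule.** This also stands. Protocol 5.2.4 allows related AEs ongoing at withdrawal to be followed for three months or more, and at 35 days the end-month rule is right for 322 of 365. A late imputed end also matches the SAP's choice of the last day of the month when the end day is missing.

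A reader might go further than the documents allow in three ways:

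- **Taking the failure rate from the pivotal study.** Protocol 9 gives a median of 2 to 4 days, which would mean failure for about nine in ten starts. That figure describes injection-related reactions. The related AEs are described separately, some with delayed onset, and without a duration.
- **Reading the end-year rule as generally broken.** It is right for 2- to 4-day AEs that start on the treatment day.
- **Concluding that December starts give ends before the start.** This needs the recorded year to be kept while the month rolls over to January. The SAP's start-month example advances the year with the month, which points the other way.

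**Conclusion.** The rules are wrong as written, and the point is minor. The end-month rule is the main defect: it fails for every AE contained in one calendar month, so its failure rate runs from 365 of 365 at 1 day to 41 of 365 at 28 days. The end-year rule fails only for AEs that end on their start date and, if enrolment spans a year end, for AEs that start in the calendar year after treatment. The start-day rule fails only when the recorded start month is later than the treatment month.

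The counts rest on the assumed 365-day window and on the assumed durations, and apply only once a rule is reached. The consequence is confined to descriptive onset and duration of related AEs with partial dates (and analysis day, if it is derived from them). AE counts, the dates as listed and the primary endpoint are unaffected.

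**What to change.** Amend SAP 10.1.2.1 as follows.

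- **End month missing:** use the AE start month if the resulting date is on or after the start date; otherwise the next month, advancing the year if needed.
- **End year missing:** use the AE start year if the resulting date is on or after the start date; otherwise the next year.
- **Start day missing:** use the treatment date if it falls in the recorded month; otherwise the first day of the recorded month when that month is after treatment.
- **Otherwise:** if no valid date with the end on or after the start results, leave the date unimputed.

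The revised end-month rule is right for 365 of 365 start dates at each duration tested from 1 to 28 days (1, 2, 3, 4, 7, 14 and 28). The cost is a few words of SAP text and a few lines of derivation code.

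There are three downsides. AEs longer than about a month with a missing end month will be imputed too short: at 35 days the revised rule is right for only 7 of 365 starts (where the recorded day does not exist in the start month), against 322 for the current rule. This can be reduced where the record shows the AE still ongoing at a later contact, but Protocol 12.1.2 lists a single outcome per AE, so such a record cannot be assumed. The first-of-month start understates onset: for onset 14 days after treatment that falls in the next month, by 0 to 13 days, mean 6.5. A few events may drop out of the duration summary.
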